When I first proposed to do TMS in the scanner over 20 years ago the MUSC IRB required that I be the first test subject, and report back. I did that and am prepared to do that here if that is what is needed. I think this LIFUP is as safe as diagnostic ultrasound, and has enormous research and clinical potential.)

Specific Aims.

- Aim 1.** Test the safety and feasibility of LIFUP to thalamus in healthy volunteers.
- Aim 2.** Characterize the time course and magnitude of thalamic LIFUP-induced analgesia.
- Aim 3.** Identify the brain circuitry (BOLD activity) that thalamic LIFUP changes during induced pain.

Hypothesis.

The anterior nuclei of the thalamus in addition to periaqueductal gray (PAG) and rostral ventromedial medulla (RVM) are integral regions of a supraspinal opioidergic structure that regulate pain perception (4-8). With the capability to influence deep neurological tissues, low intensity frequency ultrasound pulsation can likely modulate this circuit and induce analgesia. LIFUP deep brain modulation is achieved by induction of focused mechanical waveforms that traverse the cranium and underlying brain tissue (19). The low frequency of the ultrasonic wave consequently alters neuronal transmission and causes action potential variations through mechanical means, rather than thermal (20). The purpose of this study is to examine whether stimulation of the anterior nuclei of the thalamus via LIFUP induces analgesia. **We hypothesize that suppression of the anterior nuclei of the thalamus will induce a temporary increase**

in pain tolerance. Moreover, the behavioral changes in pain will correlate with specific regional BOLD changes during pain.

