10.0 Study Design/Methods

10.1. Study Design. Twenty healthy volunteers between 18-65 years of age without history of depression or chronic pain will be recruited to participate in this sham-controlled, double-blind crossover study, all within one session within the MRI scanner. All participants will receive 10 minutes of sham LIFUP, 20 minutes of rest, and 10 minutes of real LIFUP within the MRI scanner using the BXPulsar 1001, Brainsonix Inc. The order will be counterbalanced. The duration of the LIFUP analgesia and BOLD effects will be determined.

10.2. Behavioral Measures. We will begin baseline pain assessments by administering cutaneous hot and cold stimuli via the Medoc Pathway System (Medoc, Durham, NC) using a 30 x 30 mm ATS thermode. There will be two behavioral measures: quantitative sensory testing (QST) on untreated skin and blocks of pain on capsaicin-treated skin.

QST will be done using method of limits testing on the thenar eminence of the right hand. A program will be set up to administer 10 hot stimuli with random durations between each trial. The ATS thermode begins at 32°C and increases by 0.5°C per second. Participants will be asked to press a button in order to signify three different measures: (1) sensory threshold, or the temperature at which the stimulus becomes noticeable, (2) pain threshold, or the temperature at which the stimulus becomes painful, and (3) pain tolerance, or the temperature at which the stimulus becomes too painful to tolerate. Measuring these thresholds will yield information about

A β , A δ , and C fibers, respectively. The device will be set to stop heating at 51.5° C and stop cooling at 0° C to avoid tissue damage. These ten trials will be performed once before and once after each scanning block, either with thalamic LIFUP or 'fake' thalamic LIFUP.

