Blocks of pain will be administered with an adaptation of an established heat/capsaicin model (27). First, 1% capsaicin cream will be applied to a 40 x 40 mm region of skin 12 cm away from the wrist on the right volar forearm. After 30 minutes, the capsaicin cream will be cleaned off and cutaneous heat stimuli will be applied via the Medoc Pathway System using a 30 x 30 mm ATS thermode. Pain ratings will be assessed by administering 22 s blocks of pain at a temperature that each participant reports at baseline to be 7 out of 10 on a pain visual analog scale. This temperature, individualized for each participant at baseline using the PEST procedure, will be administered throughout the experiment. Studies have shown that stimuli rated as 7 out of 10 produce highly reproducible results in terms of pain ratings and fMRI activation without posing significant risk to participants (28). The device will be set to stop heating at 51.5° C to avoid tissue damage. After each heating trial, participants will rate the intensity of the pain from 1-10. The temperature rated as "7 out of 10" at baseline will be administered 12 times during the baseline scan, 12 times during the scan following sham LIFUP and 12 times during the scan following real LIFUP. These procedures have been used previously in IRB-approved studies.

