10.3. Magnetic Resonance Imaging (MRI). A Siemens 3T Trio MRI scanner will be used for imaging. After QST testing, the MR compatible ATS thermode will be placed on the capsaicin-treated right volar forearm. Participants will undergo standard high-resolution anatomical scans prior to undergoing functional scans during which 22 second blocks of heat will alternate with 22 second blocks of rest. These heat stimuli were previously rated as "7 out of 10" in intensity during baseline testing. Each fMRI scan will involve 12 pain/rest blocks. At the end of the functional scan, each participant will rate the intensity of the pain that they experienced. The functional pain/rest scan will be repeated three separate times throughout the experiment: (1) at baseline, (2) after 20 min of sham LIFUP, and (3) after 20 min of real LIFUP. A short interleaved LIFUP-fMRI scan will be performed immediately before the pain/rest block scans after sham LIFUP and real LIFUP. During these sessions, the LIFUP machine will fire single pulses at 1Hz frequency. A TR delay will be used to minimize LIFUP-induced destruction of acquired scan data. E-Prime software will be used to trigger LIFUP pulses and coordinate them with scanner TR delays. The purpose of the interleaved LIFUP-fMRI sequence is to examine how LIFUP affects BOLD signal changes in real time.

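### Section 10.1 promises the duration of LIFUP analgesia and BOLD effects, but one pain scan and one QST set after each condition cannot give the duration of an effect that outlasts them

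*Combined protocol and SAP*

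**What the plan says.** Two statements set the promise. Aim 2 (section 1.0) is to "Characterize the time course and magnitude of thalamic LIFUP-induced analgesia". Section 10.1 goes further: "The duration of the LIFUP analgesia and BOLD effects will be determined". Neither is limited to a stated period.

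The measurements are in sections 10.2 and 10.3:

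- **Pain scans.** "The functional pain/rest scan will be repeated three separate times throughout the experiment": at baseline, after sham and after real LIFUP. "Each fMRI scan will involve 12 pain/rest blocks", in which "22 second blocks of heat will alternate with 22 second blocks of rest". Section 10.2 confirms that the individualised heat stimulus is given "12 times during the scan following real LIFUP", and likewise after sham and at baseline.
- **QST.** "These ten trials will be performed once before and once after each scanning block". The thermode starts at 32°C and "increases by 0.5°C per second", with a cut-off at 51.5°C. Pauses between trials are random and their length is not given.
- **Interleaved scan.** Section 10.3 places a short LIFUP-fMRI scan, of unstated length, just before the pain scan in each condition.

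For analysis, section 12.0 plans a repeated measures ANOVA with time and condition but does not list the levels of time. Section 12.1 fits a boxcar model and takes a task-minus-rest contrast map per subject to the group level. No definition of duration, return-to-baseline criterion or serial follow-up is described.

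**The concern.** To determine a duration, one must observe the effect ending, or at least have readings late enough that it would have ended in most participants. Here the readings after each condition are few and stop soon after stimulation. If the effect is still there at the last of them, its end is right-censored. Effects lasting 30 and 60 minutes could then give the same post-condition data.

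What is at stake is the claim made under Aim 2. A flat profile over the scan could be reported as an effect that lasts, although the study neither observed its end nor specified an analysis that would support the statement. For BOLD, the planned model does not look at change over time even within the scan.

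**Working it through.** **1. Length of the pain scan.** Inputs from sections 10.2 and 10.3: 12 heat stimuli per scan, 22 s heat, 22 s rest.

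- The document's own figure is a scan of 8 minutes (motion criterion, section 12.1).
- 12 × (22 + 22) s = 528 s = 8.8 min.
- Without a final rest block: 12 × 22 + 11 × 22 = 506 s = 8.4 min.
- Reading the 12 blocks as 6 heat and 6 rest gives 6 × 44 = 264 s = 4.4 min. The 12 heat stimuli per scan rule this out.

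The stated 8 minutes is a loose rounding of 8.4 to 8.8 min, and nothing below depends on the difference.

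**2. Length of one QST set.** Inputs from section 10.2: 10 hot stimuli, start 32°C, rate 0.5°C/s, cut-off 51.5°C.

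- Longest ramp: (51.5 − 32) / 0.5 = 39 s.
- Ten ramps: 10 × 39 = 390 s = 6.5 min at most, without pauses.

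**3. End of the window after stimulation.** The pauses and the length of the interleaved scan are not stated, so the values below are assumptions. The formula is: interleaved scan + 8.8 min + 10 × (39 s + pause) / 60.

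| Assumed interleaved scan | No pause | 10 s pause | 30 s pause |
|---|---|---|---|
| 0 min | 15.3 min | 17.0 min | 20.3 min |
| 5 min | 20.3 min | 22.0 min | 25.3 min |

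**4. Readings inside that window.** Per condition there are up to 12 pain ratings over 8.8 min, one BOLD run and one post-block QST set. The ratings come from capsaicin-treated forearm and the QST from untreated skin of the hand, so they are separate outcomes and do not form one continuous series.

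**5. Any later reading.** The QST before the second block could serve as a later reading for the first condition. It informs real LIFUP only in participants who receive real LIFUP first (about half, as the order is counterbalanced). Its timing is not stated, and it is also the baseline for the next condition. In sham-first participants nothing described follows the last QST set. One such point does not determine a duration.

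**6. Planned analysis.** The time factor in section 12.0 could mean before/after or block number; the text does not say. In section 12.1 each scan yields one average task-minus-rest contrast, with no regressor for block position, so a change in BOLD response during the scan is not estimated.

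**7. Are the ratings there?** Section 10.2 has a rating after each heat trial. Section 10.3 describes a rating at the end of the scan. Both may be intended, but the text does not say so. If only the end-of-scan rating is taken, there is no within-scan course of ratings at all.

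**The case against.** Every study is censored at its last observation, and duration is neither the primary nor the secondary endpoint in section 4.0. Aim 2 speaks of time course and magnitude, which ratings after each trial can partly describe, and the undefined time factor in section 12.0 may already mean block number. All of this is fair. It makes the overclaim sharper in section 10.1 than in Aim 2, and it means fading within the scan could be seen. It does not supply a duration for an effect that has not faded by then, nor any BOLD analysis over time.

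A reader might infer more than the documents support:

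- *That the observation window is shorter than the 20-minute rest.* This holds only if pauses and the interleaved scan are ignored; under the assumptions above the window can reach 20 to 25 min.
- *That nothing is measured later.* The QST before the second block is a possible later reading for the first condition.
- *That the plan contains no analysis of time.* Section 12.0 names a time factor; the fault is that its levels are missing.
- *That a long-lasting effect would be absorbed into the next condition.* This depends on both conditions falling in one session, as section 10.1 says, whereas section 5.0 pays for scanning sessions at Visit 2 and Visit 3. Until that is reconciled the inference is not secure, and it is a separate matter from whether duration can be measured.

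**Conclusion.** The point holds. Section 10.1 claims a property that the described schedule does not have: an effect outlasting the last reading has no determinable duration. The number of readings after each condition (one pain scan, one QST set) is stated and does not depend on assumptions. The length of the window does: 15.3 min with no pauses and no interleaved scan, and 20.3 to 25.3 min with an assumed 5-min interleaved scan and pauses of 0 to 30 s. It cannot be fixed more closely because sections 10.1 and 10.3 differ on LIFUP length (10 versus 20 min) and sections 5.0 and 10.1 differ on session structure.

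The matter is moderate. It leaves the primary endpoint in section 4.1 untouched but misstates what Aim 2 can deliver.

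**What to change.** 1. Replace the duration sentence in section 10.1 with: *the magnitude of analgesia, and its change over the pain scan and QST set that follow each condition, will be estimated*. Align Aim 2 with it.
2. Limit the BOLD claim to the average effect in the post-condition scan, unless a block-by-time (parametric) regressor is added to the first-level model in section 12.1.
3. In section 12.0, define time for the ratings as block number (1 to 12). Prespecify a two-sided condition × block test with both factors within subject. Report the real-minus-sham difference early and late in the scan, with confidence intervals.
4. State that a non-significant interaction is not evidence that the effect persists, and that no duration beyond the last observation will be claimed. With 20 participants (section 10.1) or 35 (section 6.0), failure to detect fading may simply reflect imprecision.
5. Confirm that the ratings after each trial (section 10.2) are collected in addition to the end-of-scan rating (section 10.3). If they are not, item 3 cannot be done and the claim must be narrowed to magnitude in the scan and change in QST.
6. Reconcile the passages on session structure and LIFUP length (sections 5.0, 10.1 and 10.3), and state the assessment times.

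The cost is a less ambitious Aim 2, one prespecified interaction and, if chosen, one extra regressor. No additional scans, visits or participant burden are needed.

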12.0 Data Management

The behavioral pain measures will be examined using a repeated measures ANOVA with time and condition (LIFUP, sham) as between group variables. These will be paired data within each subject.

Justification of Sample Size: Prior studies by our group using this same paradigm have shown differences in pain intensity with prefrontal TMS, or blocking of opiates. (29)

Consent procedures will be carried out within a private room inside the IOP. Data acquisition will be performed within the MUSC CBI research scanner at [name] The data will not be labeled with identifiable information. Participants will be identified on all research records solely by a number, ensuring confidentiality of all data. Any information that is obtained in connection with this study and that could identify the participants will remain confidential and will not be released or disclosed without their further consent, except as specifically required by law. If the results of this research are presented at scientific meetings, participant identity will not be

disclosed. All conversations with participants will take place behind closed doors in front of only the participant and designated caregivers, family, or friends.

Any imaging or other research data will be stored in a de-identified manner.

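### QST pain tolerance is right-censored at the 51.5 °C device stop, and the planned ANOVA has no rule for trials that reach the stop without a press

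*Combined protocol and SAP*

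**What the plan says.** All references are to the combined protocol and SAP.

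- **Hypothesis (section 1.0).** "We hypothesize that suppression of the anterior nuclei of the thalamus will induce a temporary increase" and the sentence continues "in pain tolerance. Moreover, the behavioral changes in pain will correlate with specific regional BOLD changes during pain". Aim 2 in the same section is to describe the time course and magnitude of the analgesia.
- **Measure (section 10.2).** Quantitative sensory testing (QST) yields three button-press temperatures. The third is "pain tolerance, or the temperature at which the stimulus becomes too painful to tolerate". On the ramp: "The ATS thermode begins at 32°C and increases by 0.5°C per second". On the number of trials: "A program will be set up to administer 10 hot stimuli with random durations between each trial". The set of ten is run before and after each scanning block, real and sham.
- **Limit (section 10.2).** "The device will be set to stop heating at 51.5° C and stop cooling at 0° C". The stated reason is to avoid tissue damage.
- **Analysis (section 12.0).** "The behavioral pain measures will be examined using a repeated measures ANOVA", with time and condition as factors.
- **Primary endpoint (section 4.1).** Pain ratings to hot and cold stimuli. Tolerance is not named there.

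No section says what is recorded when the ramp ends without a press. None asks for a count of such trials or gives a censored-data method.

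**The concern.** A tolerance trial that ends at the device stop shows only that tolerance is 51.5 °C or higher. An ANOVA needs one number per observation, so someone has to decide what to do with such a trial, and the plan does not. The two obvious choices are to enter 51.5 or to treat the trial as missing. Both pull down the mean of the condition with the higher tolerances. The hypothesis predicts that this is the LIFUP condition, so the error would run against the predicted effect. Tolerance is also the highest of the three QST temperatures by definition, and so the most exposed to the limit.

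At stake are the estimated size of the LIFUP effect on tolerance, which Aim 2 seeks, and some power. With no written rule, the choice could also be made after the data are seen.

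**Working it through.** **Inputs from the documents.** Start 32 °C, ramp 0.5 °C per second, stop 51.5 °C, ten trials per session (section 10.2). The stop is reached after (51.5 − 32)/0.5 = 39 s. The number of participants is 20 in section 10.1 and 35 in section 6.0, so both are used.

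**Inputs not in the documents.** Mean and SD of tolerance, the expected rise, and the share of capped trials. Section 12.0 justifies the sample size only by citing earlier work, so the plan has no figure to reproduce. Everything below except the direction rests on assumed ranges.

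**Direction.** Let a be true tolerance under LIFUP and s under sham, with a ≥ s. Then min(a, 51.5) − min(s, 51.5) ≤ a − s. The inequality is strict once a exceeds both 51.5 and s. This needs no distributional assumption.

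**Size if 51.5 is entered.** For normal tolerance with mean μ and SD σ, and z = (51.5 − μ)/σ:

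E[min(X, 51.5)] = μΦ(z) − σφ(z) + 51.5(1 − Φ(z))

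Worked case, assuming σ = 1.5, sham mean 50 and a true rise of 0.5:

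- Sham: z = 1.000, so 50 × 0.8413 − 1.5 × 0.2420 + 51.5 × 0.1587 = 49.875.
- LIFUP: z = 0.667, so 50.5 × 0.7475 − 1.5 × 0.3194 + 51.5 × 0.2525 = 50.273.
- Observed rise 50.273 − 49.875 = 0.398, which is 0.398/0.5 = 80% of the true rise. Capped shares are 16% (sham) and 25% (LIFUP).

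With the same SD and rise, 99.8% is retained at a sham mean of 47 °C, 93% at 49 °C and 57% at 51 °C.

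Indexed instead by the share of control trials capped, for a true rise of 0.5 or 1.0 °C and SD 1 or 2 °C:

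| Control trials capped | Share of true rise retained |
|---|---|
| 1% | 96-99% |
| 2% | 93-97% |
| 5% | 86-94% |
| 10% | 77-88% |
| 20% | 63-76% |
| 30% | 51-65% |

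**Size if capped trials are dropped.** The mean becomes μ − σφ(z)/Φ(z). Over the same settings, 67-78% of the rise is retained at 5% capped and 57-68% at 10%. Dropping loses more than entering 51.5.

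**Power and type I error with 51.5 entered.** Simulated paired t-test on means of ten trials; 4,000 replicates, two-sided 5%, true rise 0.5 °C. Assumed SDs: participant 1.5, session 0.7, trial 0.7.

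| n | Sham mean | Power without cap | Power with cap |
|---|---|---|---|
| 20 | 49 °C | 52% | 50% |
| 20 | 51 °C | 54% | 38% |
| 35 | 49 °C | 78% | 76% |
| 35 | 51 °C | 79% | 61% |

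With no true effect, rejection with the cap stayed between 4.6% and 5.5%.

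**Check on the remedy.** The ten trials of a session share that session's variation. A trial-level model with only a participant random effect ignores this. In its uncensored equivalent, with no true effect, two conditions of ten trials and the SDs above, type I error was about 48% at n = 20. With session SD 0.3 it was about 22%. A paired test on session means stayed near 5%. Any trial-level model therefore needs a session effect.

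**The case against.** The strongest reply is that the documents show no wrong analysis. A reader might infer that the plan enters 51.5 as an exact tolerance; no section says so. What can be shown is that a rule is missing. This stands, and the point is worded accordingly. It does not remove the need for a rule, since dropping the trials also understates the rise.

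A second reply is that nothing shows the limit is reached often. This also stands. If 1-2% of control trials are capped, 93-99% of the rise survives, and with a mean near 47 °C the loss is trivial.

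Third, a reader might infer that the primary test is compromised. Section 4.1 names pain ratings, and section 10.2 collects 1-10 ratings after heat blocks at a fixed, individualised temperature. The QST ramp stop does not censor those ratings. Tolerance is the variable in the hypothesis, and the protocol does not reconcile the two, but the listed primary endpoint is not affected.

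Fourth, a censored model has costs of its own. It relies on normality above the cap, where the data cannot check it, and without a session effect it could do more harm than the cap. Both objections are met by the form of the fix.

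**Conclusion.** The point holds as a gap in the analysis plan. Tolerance is right-censored at 51.5 °C, no rule covers capped trials, and either simple handling understates a true rise. The direction is arithmetic; the size is not known. Under the assumed normal distribution, rise and SD, with 51.5 entered, the share of the rise retained runs from 96-99% (1% of control trials capped) to 51-65% (30% capped). Whether the loss is negligible or material depends on a capped share that the documents do not give.

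The documents do not support reading this as a source of false positives: with no true effect the two conditions are capped alike, and the simulated error rate stayed near 5%. Nor is it a criticism of the safety limit. It is a minor, inexpensive improvement that bears on the hypothesis variable and on the magnitude sought in Aim 2.

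**What to change.** 1. For each QST trial, record whether the 51.5 °C stop was reached without a press. Set this up before data collection, because a press close to 51.5 °C may not be distinguishable from a device stop afterwards.
2. Report the number of capped trials by condition and time.
3. State in section 12.0 that, if any tolerance trial is capped, the LIFUP-sham difference will be estimated with a right-censored (Tobit) mixed model. It should have random effects for participant and for session (participant by condition by time), and be shown beside the planned ANOVA on session means, with the handling of capped trials in that ANOVA also stated.

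If no trial is capped, the censored model reduces to the ordinary mixed model. The cost is one flag per trial and a somewhat more complex model. The downsides are somewhat wider intervals when many trials are capped and reliance on normality above the cap. The device limit is unchanged.

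### QST has its own pre-block value in each condition, but the planned ANOVA names no test term and no baseline covariate; if time means pre/post, its interaction is valid but less precise than a baseline-adjusted contrast unless r is high

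*Combined protocol and SAP*

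**What the plan says.** Section 10.2 measures sensory threshold, pain threshold and pain tolerance by QST: "These ten trials will be performed once before and once after each scanning block", whether the block is real or sham. Each condition therefore has its own pre-block and post-block value.

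Section 10.1 describes a crossover within one session: "All participants will receive 10 minutes of sham LIFUP, 20 minutes of rest, and 10 minutes of real LIFUP within the MRI scanner". It adds: "The order will be counterbalanced".

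The whole behavioural analysis is in section 12.0: "The behavioral pain measures will be examined using a repeated measures ANOVA with time and condition (LIFUP, sham) as between group variables". The next sentence reads "These will be paired data within each subject". The section does not define the levels of time, say which term tests LIFUP, or mention a covariate, a change score, period or sequence.

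**The concern.** A pre-block value has been collected for each condition, and the plan does not say how it enters the treatment comparison. On the natural reading, pre and post are the two levels of time. The pre-block value is then a second level of the outcome and not a covariate, and the three F-tests answer different questions. Only the time-by-condition interaction estimates the LIFUP effect in full. It does so through raw change scores, which can be noisier than a comparison that ignores the baseline.

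At stake is precision for pain tolerance, the variable in the section 1.0 hypothesis, in a study for which no power calculation is given. There is also a risk that the wrong F-test is reported as the test of LIFUP.

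**Working it through.** **Inputs from the documents.** QST before and after each block (10.2); two conditions, counterbalanced, with 20 minutes of rest between them (10.1); N = 20 (10.1) or 35 (6.0). No effect size, SD, alpha, power or correlation is stated, so neither sample size can be reproduced.

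**Assumptions.** Time means pre/post. Two-sided alpha is 0.05. The effect is 0.66 SD of the post-block real-minus-sham difference, a size that gives the unadjusted post-block difference 80% power at N = 20. r is varied.

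**Set-up.** For each participant, let Dpre and Dpost be the real-minus-sham differences before and after the block, each with variance V and correlation r. Without carryover, E[Dpre] = 0 and E[Dpost] = δ.

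**Estimators, variance per participant.**
- Interaction, mean of (Dpost − Dpre): expectation δ, variance 2(1 − r)V.
- Unadjusted post-block difference: expectation δ, variance V.
- Baseline-adjusted (ANCOVA), the intercept of Dpost regressed on Dpre: expectation δ, variance (1 − r²)V.
- Condition main effect, mean of (Dpre + Dpost)/2: expectation δ/2, variance (1 + r)V/2.

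**Variance ratio, interaction to ANCOVA.** 2(1 − r)/(1 − r²) = 2/(1 + r). This is 1.54 at r = 0.3, 1.33 at 0.5, 1.18 at 0.7 and 1.05 at 0.9. Below r = 0.5 we have 2(1 − r) > 1, so the interaction is also less precise than ignoring the baseline.

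Estimating the slope multiplies the ANCOVA variance by about 1 + 1/(N − 3), which is 1.059 at N = 20. At r = 0.9 this cancels the gain: 1.05/1.059 ≈ 0.99.

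**Power at N = 20 and r = 0.3.** Here 0.66 × √20 = 2.95.
- Interaction: noncentrality 2.95/√1.4 = 2.49 on 19 df, power 66%.
- ANCOVA: 2.95/√(0.91 × 1.059) = 3.01 on 18 df, power 81%.
- Unadjusted post-block difference: 2.95 on 19 df, power 80%.
- Condition main effect: (2.95/2)/√0.65 = 1.83 on 19 df, power 41%.

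The same formulas give:

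| N | r | Interaction | ANCOVA | Unadjusted post-block |
|---|---|---|---|---|
| 20 | 0.3 | 66% | 81% | 80% |
| 20 | 0.5 | 80% | 88% | 80% |
| 20 | 0.7 | 95% | 97% | 80% |
| 35 | 0.3 | 89% | 97% | 97% |

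Simulation agrees on the ANCOVA figures at N = 20 (81% at r = 0.3, 88% at r = 0.5). Adding a period term costs less than one percentage point. Simulation also puts the condition main effect at 0.496, 0.502 and 0.500 of δ at r = 0, 0.4 and 0.8.

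**Carryover.** Suppose real LIFUP leaves an amount c in the second pre-block value of participants who receive it first (half of them). Then E[Dpre] = −c/2.
- If c persists equally to the post-block value, the change score gives δ, ANCOVA gives δ − (1 − r)c/2, and the unadjusted difference gives δ − c/2.
- If c has gone by then, the change score gives δ + c/2, ANCOVA gives δ + rc/2, and the unadjusted difference gives δ.

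With c = 0.25δ and r = 0.4, ANCOVA gives 0.925δ in the first case and 1.05δ in the second. The change score gives 1.00δ and 1.125δ. No single estimator is best in both cases.

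**The case against.** **Time is undefined.** The plan never says that pre and post are its levels. Aim 2 concerns a time course, so another meaning is possible. This stands, and the point is conditional on the pre/post reading. Under any other reading, the use of the pre-block values is still unspecified.

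**The interaction is a valid, conventional test.** This stands. A reader might infer that the planned LIFUP test captures only half the effect. The documents do not support that, because no passage makes the condition main effect the treatment test.

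**The loss depends on an unknown r.** This also stands. It is small at r = 0.7 and gone by about r = 0.9 at N = 20. Stable differences between people cancel in Dpre and Dpost, so a high r cannot be presumed either. At low r, adjustment gains on the interaction but hardly on ignoring the baseline (81% against 80% at r = 0.3).

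**ANCOVA is not uniformly safer under carryover.** Correct: it is less biased than the change score only if carryover has faded by the post-block measurement.

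**The primary endpoint is pain ratings (4.1).** QST yields temperatures, and the capsaicin-block ratings share one baseline scan (10.2). A reader might infer that the primary analysis is affected; the documents do not establish that.

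**Conclusion.** The point holds as a matter of efficiency and specification for QST. Section 12.0 names no test term, does not say how the pre-block value is used, and calls within-person factors between-group. That label alone does not show that the data would be analysed as independent groups, since the next sentence calls them paired.

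On the pre/post reading, the interaction has 2/(1 + r) times the variance of the baseline-adjusted contrast. Under the assumed 0.66 SD effect this costs about 15 percentage points of power at N = 20 and r = 0.3, 8 at r = 0.5 and 2 at r = 0.7. At N = 35 and r = 0.3 it costs about 8. The algebra assumes equal pre- and post-block variances and no carryover. The practical loss cannot be settled from the documents, which give neither r nor an effect size.

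**What to change.** In section 12.0:
- Treat time and condition as within-subject factors and define the levels of time.
- For each QST measure, name one treatment contrast: the post-block real-minus-sham difference, adjusted for the pre-block real-minus-sham difference and for period (order). Read it at a pre-block difference of zero, with order coded symmetrically.
- State that the time and condition main effects are not tests of LIFUP.
- Report the unadjusted post-block difference and the change-score interaction as sensitivity analyses, because the second pre-block value follows the first condition after only 20 minutes of rest and the direction of any bias depends on whether carryover persists.

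The cost is a few sentences and one or two degrees of freedom. No new data are needed.
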